### **8.3. Enrollment**

A subject is considered enrolled when the consent is provided. The date the subject signed the IC must be documented in the subject's medical records. Enrollment can be a stand-alone visit or can occur on the same day as the baseline visit. Once consent is obtained, a subject identification number will be assigned and data collection on adverse events (AEs), study deviations and subject exits will occur.

### **8.4. Baseline (Day -28 to 0)**

When a subject is consented, the principal investigator will review the subject's medical record and confirms if they meet all specified inclusion criteria and none of the exclusion criteria. The baseline visit

*Medtronic Business Restricted*

**CONFIDENTIAL**

056-F275 Rev E Clinical Investigation Plan Template

can be a stand-alone visit or can be performed on the same day prior to the surgical procedure. The following information is required to be collected at the baseline visit:

- Enrollment status: Date of consent, eligibility check
- Demographics: Sex (male/female), date of birth, height (cm), weight (kg), body mass index (BMI)
- Medical history: Comorbidities or past surgical history (within the last year), family history of study indication (i.e., prostate cancer, cholelithiasis, cholecystitis, or gallbladder polyps), ASA class [13]
- Laboratory tests: Complete blood cell, serum chemistry (e.g., Complete blood cell (RBC, WBC, Hb, Hct, Platelet, ESR, etc.), admission panel (Glucose, Calcium, Phosphorous, BUN, Uric acid, Creatinine, eGFR (MDRD), AST, ALT, ALP, Total bilirubin, Albumin, Total protein, etc.), electrolyte panel (Sodium, Potassium, Chloride, etc.), hs-CRP
- Vital signs: pulse rate (bpm), respiration rate (bpm), blood pressure (mmHg), body temperature (°C)
- Indication under study: Date of diagnosis (i.e., prostate cancer, cholelithiasis, cholecystitis, or gallbladder polyps), and following items (collected per indication)
  - Prostatectomy: Prostate volume (g), Biopsy Gleason score [14], PSA (ng/mL), clinical stage per AJCC rules [15], prior neoadjuvant hormonal therapy
  - Cholecystectomy: Concomitant bile duct stones, ERCP
- Prior medications: Brand name, indication (see Section 8.9 for details)
- Adverse event (if any): Diagnosis, seriousness, severity, action taken, outcome, relatedness, etc.

## 8.5. Surgical Procedure (Day 0)

The subject will arrive for admission to the hospital and prepped for surgery. On the day of surgery, the subject will receive a robotic assisted prostatectomy or cholecystectomy per indication. Pre-operative and operative procedures are according to local standard practices. The following information is required to be collected at the surgery visit:

- Pre-operative vital signs: pulse rate (bpm), respiration rate (bpm), blood pressure (mmHg), body temperature (°C)
- Procedure information
  - Date of admission, date of surgery

- Operative time: Setup time, console time, total operative time (skin to skin time), takedown time
- Estimated blood loss (mL)
- Conversion: Conversion to open/laparoscopic surgery during procedure (and reason for conversion, if conversion occurs)
- Blood transfusion: Blood transfusion during surgery (and the number of blood pack used if transfusion required)
- Changes to port placement (and reason for change, if occurs)
- Delay in robot setup time or total operative time (and reason for delay, if occurs)
- Device information: Lot number, software version, compatible instruments
- Other measurements: Collected per indication
  - Prostatectomy: Pelvic lymph node dissection, nerve-sparing prostatectomy
  - Cholecystectomy: Amount of gallbladder adhesions, concomitant gallbladder stones, type of gallbladder polyps (if applicable), acute cholecystitis, other concomitant procedures, use of drainage tube
- Medication: Brand name, indication (see Section 8.9 for details)
- Adverse event (if any): Diagnosis, seriousness, severity, Clavien-Dindo grade, action taken, outcome, relatedness, etc.
- Device deficiency (if any): Diagnosis, applicable device information (e.g., device type, Lot number, etc.)

In addition to above, below information is to be collected immediately after prostatectomy.

- Laboratory tests: Complete blood cell, serum chemistry (e.g., Complete blood cell (RBC, WBC, Hb, Hct, Platelet, ESR, etc.), admission panel (Glucose, Calcium, Phosphorous, BUN, Uric acid, Creatinine, eGFR (MDRD), AST, ALT, ALP, Total bilirubin, Albumin, Total protein, etc.), electrolyte panel (Sodium, Potassium, Chloride, etc.),
- Post-operative imaging (only collected if it is related to adverse events): Chest X-ray (Chest AP) findings, abdomen supine X-ray findings

The detailed procedural steps are described below. The steps can vary based on surgeon's technique, preference, and patient's condition.

---

 Setup time is defined as sum of following durations: Time from the first robot arm plugged in to all arms fully calibrated, time spent to drape all robotic arms, and time from the movement of the first arm to the patient to all arms docked to ports.

 See Hugo Set-up Guide and Hugo User Guide for detailed information

***Medtronic Business Restricted***

## 8.5.1. Prostatectomy Procedures

The key steps in robotic radical prostatectomy are below:

[figure not shown]
- Patient positioning: The patient is prepped and draped in lithotomy and Steep Trendelenburg (>20°) position under general anesthesia.
- Port placement: Incisions for port placement are made. The camera port is placed through a periumbilical incision. Three remaining ports (i.e., left, right, and reserve) are placed at a safe distance from the camera port and/or adjacent ports. If necessary, non-robotic assist ports can be placed at a safe distance from adjacent robotic ports.
- Arm cart positioning: The robotic arms are connected to the robotic ports. The endoscope and wristed instruments are attached to robotic arms and inserted to ports.
- Dropping the bladder: The bladder is separated from the peritoneum down to the vas deferens and then deep into perirectal space. The anterior prostatic fat is dissected and further dissected off of the anterior prostatic capsule from the apex to the bladder neck.
- Endopelvic fascia: The endopelvic fascia is initially incised laterally closer to muscle than the nerve. At the apex, completely release Myer's muscle to visualize and protect the apex, neurovascular bundle (NVB), and urethra when transecting the dorsal venous complex (DVC) and remaining apical structures.
- Anterior or posterior bladder neck: The site of transection of the anterior bladder neck is visually facilitated by retracting the Foley balloon. Transection of the bladder from the prostate.
- Seminal vesicles and rectum: The seminal vesicles are used to lift the prostate for separation from the rectum. Denonvilliers' fascia is grasped and lifted and incised sharply until the perirectal fat is seen.
- Transection of the prostatic pedicles and the NVBs: Nerve preservation with athermal coldcut resection sharply releasing the nerve from the prostate without traction.
- DVC and urethral transection: The dorsal vein and urethra are cut then oversew the DVC.
- Vesicoureteral anastomosis: Circular anastomosis between urethra and bladder.
- Specimen removal and closure: The resected prostate gland and attached seminal vesicles are removed and the incised port site is closed..
- Arm cart undocking: The arms are disconnected from the ports. The patient is moved off the table and taken to the recovery room.

*Medtronic Business Restricted*

**CONFIDENTIAL**

056-F275 Rev E Clinical Investigation Plan Template

Figure 5 describes port placement and arm cart positioning during the robotic prostatectomy. Deviations may need to be made for specific patient body habitus, patient pathology, or surgeon preference.

**Figure 5. Port Placement and Arm Cart Positioning (Prostatectomy)**

### 8.5.2. Cholecystectomy Procedures

The key steps in robotic cholecystectomy are below:

[figure not shown]
- Patient positioning: The patient is prepped and draped in reverse Trendelenburg (>20°) position under general anesthesia.
- Port placement: Incisions for port placement are made. The camera port is placed through a periumbilical incision. Three remaining ports (i.e., left, right, and reserve) are placed at a safe distance from the camera port and/or adjacent ports. If necessary, non-robotic assist ports can be placed at a safe distance from adjacent robotic ports.
- Arm cart positioning: The robotic arms are connected to the robotic ports. The endoscope and wristed instruments are attached to robotic arms and inserted to ports.
- Identification of gallbladder after insertion of endoscope: After identification of the gallbladder, the fundus is retracted cephalad over the liver with a grasping instrument.
- Dissection of cystic pedicle: Adhesions are taken down using the Maryland dissector. Using an additional grasper, the gallbladder is retracted inferolaterally to expose the triangle of Calot.
- Separation of cystic artery from cystic duct: The separation of the cystic duct anteriorly from the cystic artery behind and can be performed by a Maryland grasper.
- Clipping of cystic artery: The cystic artery is clipped and then divided by hook scissors and the dissection of the cystic pedicle is completed by placement of a clip to occlude the cystic duct.

*Medtronic Business Restricted*

- Dissection of gallbladder from liver bed: Gallbladder should be separated from the liver performed with scissors with electro-surgical attachment or Monopolar hook or knife.
- Extraction of gallbladder and closure: After completion of the gallbladder resection, it will be placed in a retrieval bag and removed through the umbilical port. All incised port site is closed.
- Arm cart undocking: The arms are disconnected from the ports. The patient is moved off the table and taken to the recovery room.

Figure 6 describes port placement and arm cart positioning during the robotic cholecystectomy. Deviations may need to be made for specific patient body habitus, patient pathology, or surgeon preference.

**Figure 6. Port Placement and Arm Cart Positioning (Cholecystectomy)**

## 8.6. Up to Hospital Discharge (After Surgery~Discharge)

The subject's condition will be closely monitored until discharge. Vital signs and laboratory test will be conducted on Day 1, 3 for prostatectomy subjects, and Day 1 for cholecystectomy subjects. AE will be collected and assessed according to Clavien-Dindo classification system. The following information is required to be collected:

- Date of discharge
- Laboratory tests: Complete blood cell, serum chemistry (e.g., Complete blood cell (RBC, WBC, Hb, Hct, Platelet, ESR, etc.), admission panel (Glucose, Calcium, Phosphorous, BUN, Uric acid, Creatinine, eGFR (MDRD), AST, ALT, ALP, Total bilirubin, Albumin, Total protein, etc.), electrolyte panel (Sodium, Potassium, Chloride, etc.), hs-CRP)

- Vital signs: pulse rate (bpm), respiration rate (bpm), blood pressure (mmHg), body temperature (°C)
- Medication: Brand name, indication (see Section 8.9 for details)
- Adverse event (if any): Diagnosis, seriousness, severity, Clavien-Dindo grade, action taken, outcome, relatedness, etc.
- Other measurements: Collected per indication
  - Prostatectomy: Date of urinary catheter removal
  - Cholecystectomy: Date of drain removal

In addition to above, below information is to be collected for prostatectomy subjects. Post-operative imaging will be conducted on Day 1 and 3, but findings will be only collected if it is related to adverse events.

- Pathological exam: Pathological stage per AJCC rules, tumor size (mm), positive surgical margin (and its location, if positive)
- Post-operative imaging (only collected if it is related to adverse events): Chest X-ray (Chest AP) findings, abdomen erect X-ray findings, KUB X-ray findings

## 8.7. Post-Operative Follow-up (Up to Day 30)

Subject will be followed through 30-day post-surgery.

### 8.7.1. Prostatectomy Subjects (Day 7, Day 14, and Day 30)

Prostatectomy subjects will be followed at 7-day ( $\pm 3$  days), 14-day ( $\pm 3$  days), and 30-day ( $\pm 7$  days) post-operative outpatient visits. The following information will be collected:

NOTE: Laboratory tests and vital sign assessments will be done at Day 14 and 30 only, and cystography will be done on Day 7 only.

- Laboratory tests (Day 14, Day 30 only): Complete blood cell, serum chemistry (e.g., Complete blood cell (RBC, WBC, Hb, Hct, Platelet, ESR, etc.), admission panel (Glucose, Calcium, Phosphorous, BUN, Uric acid, Creatinine, eGFR (MDRD), AST, ALT, ALP, Total bilirubin, Albumin, Total protein, etc.), electrolyte panel (Sodium, Potassium, Chloride, etc.), hs-CRP), PSA (ng/mL) (Day 30 only)
- Vital signs: pulse rate (bpm), respiration rate (bpm), blood pressure (mmHg), body temperature (°C)
- Post-operative imaging (only collected if it is related to adverse events): Cystography findings (Day 7 only)
- Medication: Brand name, indication (see Section 8.9 for details)
- Adverse event (if any): Diagnosis, seriousness, severity, Clavien-Dindo grade, action taken, outcome, relatedness, readmission/reoperation (and surgeon comments on the AE form if occurs), etc.

*Medtronic Business Restricted*

## 8.7.2. Cholecystectomy Subjects (Day 30)

Cholecystectomy subjects will be followed at 30-day ( $\pm 7$  days) post-operative outpatient visit. The following information will be collected:

- Laboratory tests: Complete blood cell, serum chemistry (e.g., Complete blood cell (RBC, WBC, Hb, Hct, Platelet, ESR, etc.), admission panel (Glucose, Calcium, Phosphorous, BUN, Uric acid, Creatinine, eGFR (MDRD), AST, ALT, ALP, Total bilirubin, Albumin, Total protein, etc.), electrolyte panel (Sodium, Potassium, Chloride, etc.), hs-CRP)
- Vital signs: pulse rate (bpm), respiration rate (bpm), blood pressure (mmHg), body temperature ( $^{\circ}\text{C}$ )
- Medication: Brand name, indication (see Section 8.9 for details)
- Adverse event (if any): Diagnosis, seriousness, severity, Clavien-Dindo grade, action taken, outcome, relatedness, readmission/reoperation (and surgeon comments on the AE form if occurs), etc.

## 8.8. Subject Exit, Withdrawal or Discontinuation

Subjects have the right to refuse to participate the study as well as voluntarily withdraw from the study at any time. In case of study exit, the reason and date for study exit of all enrolled subjects will be documented on the applicable page of case report form (CRF). Subjects may be exited from the study for any of the following situations:

- Study completed (i.e., completed 30-day post-operative visit)
- Subject did not provide consent
- Subject chooses to withdraw
- Subject did not meet inclusion/exclusion criteria
- Subject did not receive surgery using the investigational device
- Subject death
- Subject lost to follow-up (i.e., up to 30-day post-operative visit)
- Unacceptable AEs
- Investigator deems withdrawal necessary (e.g., medically justified, failure of subject to maintain adequate study compliance)

All AEs must be followed until the AE has been resolved, is unresolved with no further actions planned, the subject dies or exits the study, whichever occurs first. In cases of early study exits, all data collected from the time of consent to the time of exit may be used. For subjects who complete the 30-day follow-up visit, the 30-day follow-up visit and exit visit should be combined, and CRF for both need to be completed.

*Medtronic Business Restricted*

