
Study Procedures
	
The study visits include baseline visit, admission (surgery to discharge), and follow-up visit after discharge:
 
 
- Baseline: To determine study eligibility and collect baseline information (demographics, medications, medical history, surgical history, etc.)
 
- Surgical procedure: To re-confirm eligibility criteria, procedure set-up and take-down, medication changes, intraoperative complication evaluation, disease state evaluation, procedure success, conversion rates, protocol deviation, adverse event evaluation, and device deficiency collection
 
- Up to hospital discharge: Adverse event evaluation, complication rate, disease state evaluation, medication changes and protocol deviation
 
- Follow-up after discharge: Adverse event evaluation, complication rate, disease state evaluation, length of hospital stay, readmission (if applicable), reoperation (if applicable), medication changes, protocol deviation and study exit
 
 
Prior to subject enrollment, investigators who participate in surgical procedure will be properly trained on the investigational device. When a subject provides written informed consent, the principal investigator reviews the subject's medical records and confirms the eligibility criteria. The subject will be hospitalized and prepped for surgery according to site standard practices. On the day of surgery (Day 0), robot-assisted prostatectomy or cholecystectomy using Hugo™ RAS System is performed according to patient's indication. Intraoperative complication during the surgery will be monitored. For prostatectomy subjects, pathological examination on the resected specimen shall be performed.

	
Subjects will be followed through 30-day post-operative visit. Prostatectomy subjects will be followed at the day of discharge, 7-, 14-, and 30-day post-operative visits. Cholecystectomy subjects will be followed at the day of discharge, and 30-day post-operative visit. Post-operative complications will be evaluated. Subject’s study participation will be terminated when the subject expires, is lost to follow-up, or at the last follow-up visit (whichever occurs first).
																	

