## 10. Adverse Events and Device Deficiencies

### 10.1. Adverse Events and Device Deficiencies

All AEs will be collected throughout a subject's participation, starting from the time the IC is provided, regardless of their severity or relationship to the Hugo™ RAS or study procedures. Assessment of the occurrence of an AE will be based on changes in the subject's physical examination, laboratory results, and/or signs and symptoms. Reporting of these events to the sponsor will occur on an AE CRF, including date of AE, event description, treatment, resolution, assessment of both the seriousness of the AE and the relatedness to the system components. The completed AE CRF must be submitted to Medtronic as soon as possible.

In addition, DD information will be collected throughout the study and reported to the sponsor on a DD CRF. Note that DDs that result in an AE to the subject should be captured as an AE only. DD that could have led to a serious adverse device effect (SADE) (i.e., if suitable action had not been taken, if intervention had not been made, or if the circumstances had been less fortunate) require immediate reporting.

Upon receipt of AE or DD at Medtronic, a sponsor representative will review the AE/DD for completeness and accuracy and when necessary will request clarification and/or additional information from the investigator. If the event is unanticipated or unanticipated serious ADE, the sponsor will review the specific details behind those observations and determine what, if any, action is appropriate.

For any changes in status of a previously reported AE or DD (i.e., change in actions taken, change in outcome, change in relatedness), information needs to be updated on, or added to the original AE or DD CRF.

All AEs must be followed until the AE has been resolved, is unresolved with no further actions planned, the subject dies or exits the study, whichever occurs first. At the time of study exit, all collected AEs that are unresolved must be reviewed and an update to the original AE must be reported.

Adverse events that have not resolved at the time of the subject's discontinuation or completion of the study should have an outcome of Not Recovered/Not Resolved at study end in subject source and on eCRF. The investigator should ensure that subject is aware of any follow-up or additional treatment that is required for any ongoing AE at the end of study participation; however, there will be no eCRF entry for the ongoing follow-up.

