The investigator shall not withdraw a subject's study participation unless compelling medical justification is present. Every attempt will be made to complete the subject's study per the CIP, and regular telephone follow-up is acceptable to have the subject engage in study procedures. However, when the risks are found to outweigh the potential benefits or when there is conclusive proof of definite outcomes, investigators must assess whether to continue, modify or immediately stop the study in the respective site and immediately inform the sponsor and IRB, if applicable.

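### Study exit after the operation also ends safety data collection, so 30-day readmission, reoperation, escalation or death can go unrecorded in subjects exited early

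*Protocol*

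**What the plan says.** Protocol 8.8 introduces its exit list with "Subjects may be exited from the study for any of the following situations". The list includes "Unacceptable AEs", which is not defined, as well as failure to meet the eligibility criteria and the investigator's view that withdrawal is needed. No item is tied to the period before or after surgery.

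On follow-up, 8.8 states: "All AEs must be followed until the AE has been resolved, is unresolved with no further actions planned, the subject dies or exits the study". Section 10.1 repeats this rule. For events still open at discontinuation or completion, it adds: "however, there will be no eCRF entry for the ongoing follow-up".

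Two provisions keep what was recorded before exit. Section 8.8 says: "In cases of early study exits, all data collected from the time of consent to the time of exit may be used". Section 10.1 says: "At the time of study exit, all collected AEs that are unresolved must be reviewed and an update to the original AE must be reported".

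Two other places describe the end of participation differently. In the Synopsis (Study Procedures), the subject's "study participation will be terminated when the subject expires, is lost to follow-up, or at the last follow-up visit (whichever occurs first". In 12.17, under Suspension or Early Termination, the investigator may not end a subject's "study participation unless compelling medical justification is present". That section also asks for every effort to complete follow-up and accepts telephone contact.

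Four of the five secondary endpoints run to Day 30: overall complications, major complications, readmission and reoperation (Protocol 4.2.2, SAP 7.9). Missing data are not imputed for the primary analysis, and sensitivity analyses are optional (Protocol 9.1, SAP 7.4). Neither document says how a subject who exits early is counted in a 30-day rate.

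**The concern.** Exposure to the device is a single operation on Day 0. From then on the protocol only observes the subject, so exit because of an adverse event withdraws no study treatment and ends only the collection of data. The reason for exit may be the safety outcome itself or an early sign of it, which makes the loss informative.

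Protocol 8.11 names the secondary endpoints as the safety assessment of the device. With 40 subjects, and rates also reported for each group of 20, one or two unobserved outcomes change the picture. Cholecystectomy subjects have only one scheduled visit after discharge, at Day 30 (8.7.2), so an exit before it removes their only planned check for readmission or reoperation.

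**Working it through.** **The plan's own figure.** The documents give no early-exit rate and no expected 30-day rate. The only related count is in Protocol 6.5: success needs at least 0.95 × 40 = 38 completers, hence at most 2 failures. 38/40 = 95.0% passes and 37/40 = 92.5% does not, so that figure reproduces. The same section makes no dropout allowance because the primary endpoint closes at 24 hours. That reason does not carry over to endpoints at 30 days.

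**What an exit for an adverse event can and cannot remove.**

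| Endpoint | Effect of a post-operative exit for an adverse event |
|---|---|
| Primary endpoint (24 hours) | Affected only if exit falls within 24 hours |
| Device deficiency | None: determined during surgery |
| Overall complications | The triggering post-operative event already counts |
| Major complications | Already counts if the trigger is grade 3 or higher; a lower-grade event that later worsens, or a later death, can be lost |
| Readmission | Can be lost |
| Reoperation | Can be lost, if it is for the same indication as the endpoint requires |

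A subject exited for ineligibility or by investigator decision, with no complication so far, can also lose a first complication.

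**Size.** Inputs: N = 40, 20 per procedure (Protocol 7.2); exact Clopper-Pearson 95% intervals (SAP 7.9). The number of early exits, m, is an assumption, shown from 1 to 4. With x observed events:

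- exits counted as non-events: x/N
- exits dropped from the denominator: x/(N − m)
- worst case, each exit an event: (x + m)/N
- worst case minus the rate with exits counted as non-events: m/N, which is 1/40 = 2.5 points per exit overall and 1/20 = 5 points per procedure

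With x = 0 and N = 40, the reported rate is 0% under either counting rule. If exits stay in the denominator, the interval is 0 to 8.8%. The worst case is:

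| m | (0 + m)/40 | 95% interval |
|---|---|---|
| 1 | 2.5% | 0.1 to 13.2% |
| 2 | 5.0% | 0.6 to 16.9% |
| 3 | 7.5% | 1.6 to 20.4% |
| 4 | 10.0% | 2.8 to 23.7% |

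With x = 1 and m = 2, the report reads 1/40 = 2.5% or 1/38 = 2.6%, against (1 + 2)/40 = 7.5%.

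Within one procedure (N = 20, x = 0), the report reads 0% (0 to 16.8%). The worst case is 1/20 = 5.0% (0.1 to 24.9%) for m = 1 and 2/20 = 10.0% (1.2 to 31.7%) for m = 2.

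An illustration under assumed numbers: if 4 of 40 subjects truly have the event (10.0%) and 2 of them exit before it, the report reads 2/40 = 5.0%, or 2/38 = 5.3% if they are dropped.

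**Per Protocol Set.** Missing required data up to Day 30 is a reason for exclusion (Protocol 9.1, SAP 7.1.3). A subject exited for a serious event before Day 30 would therefore leave that set, and the event already recorded would go too.

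**The case against.** The strongest reply is that the plan already protects most of the data. Data up to exit may be used and open events are updated at exit. A reader might infer that subjects with the worst events drop out of the 30-day complication rates. The documents do not support that: a subject exited on Day 5 for a grade III event has already met both complication endpoints in the Full Analysis Set. This part of the reply stands in full.

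Section 12.17 is the next line of defence. If exit after surgery protects nobody, an adverse event hardly supplies a compelling medical reason for it, so such exits should be rare. That narrows the gap but does not close it. The sentence sits under study suspension, 8.8 does not refer to it, and 8.8 names adverse events as an exit reason in their own right. Section 8.13 treats failure to collect data to Day 30 as a major deviation, but that label does not recover the data.

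Three further limits are fair. The freedom to leave at any time in 8.8 belongs to the subject; it is not a licence for the investigator. The Synopsis also omits voluntary withdrawal, so its list cannot be read as exhaustive, and its mismatch with 8.8 is a matter for reconciliation more than a flat contradiction. Finally, the secondary endpoints are descriptive with no success threshold, so no pass or fail decision turns on them.

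**Conclusion.** The point holds in a limited form. As written, the exit rules permit outcome-related loss of readmission, qualifying reoperation, escalation of a lower-grade event and death between exit and Day 30, and no rule secures Day-30 status afterwards. The 30-day rates can therefore be too low, by up to 2.5 percentage points per exit overall and 5 points within a procedure. These are upper bounds. They assume that the exited subject went on to have an event that counts, and that the subject is kept as a non-event. Dropping exits from the denominator changes the result only slightly.

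A reader might go further and conclude that the rates are biased. The documents do not show this, because they give no exit frequency and there may be no such exits. The device deficiency rate is untouched, and the primary endpoint is touched only by an exit within 24 hours. The change is worth making because it is cheap and removes an avoidable doubt about the safety results.

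**What to change.** 1. Reconcile the Synopsis (Study Procedures), 8.8, 10.1 and 12.17 on when participation and follow-up end.
2. State in 8.8 and 10.1 that, once the first skin incision has been made, exit for an adverse event, ineligibility or investigator decision does not end safety data collection. This concerns data only; clinical care and the subject's right to withdraw are unchanged.
3. For every Full Analysis Set subject, collect Day-30 vital status, complications with Clavien-Dindo grade, readmission and reoperation, unless consent is withdrawn or the subject is lost to follow-up. Use the telephone contact that 12.17 already accepts where a visit is not possible.
4. In the SAP, list any remaining early exits and show, beside each observed 30-day rate, a worst-case bound that counts each of them as an event, overall and by procedure.

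The cost is a wording amendment, a few extra follow-up contacts and one extra table. No additional patients or procedures are needed.
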